### 2.2.1. Primary Efficacy Objective

- *To assess the efficacy of SA4Ag in the prevention of postoperative S aureus BSI and/or deep incisional or organ/space SSI occurring within 90 days of elective open posterior instrumented spinal fusion procedures with multilevel instrumentation, in adults aged 18 to <86 years.*

### 2.2.2. Primary Safety Objective

- *To describe the safety and tolerability of a single vaccination of SA4Ag in adults aged 18 to <86 years undergoing elective open posterior instrumented spinal fusion procedures with multilevel instrumentation, by measuring local reactions, systemic events, and adverse events (AEs).*

### 2.2.3. Secondary Efficacy Objectives

- *To assess the efficacy of SA4Ag in the prevention of postoperative S aureus BSI and/or deep incisional or organ/space SSI occurring within 180 days of elective open posterior instrumented spinal fusion procedures with multilevel instrumentation, in adults 18 to <86 years of age.*
- *To assess the efficacy of SA4Ag in the prevention of postoperative S aureus SSI occurring within 90 days of elective open posterior instrumented spinal fusion procedures with multilevel instrumentation, in adults 18 to <86 years of age.*
- *To assess the efficacy of SA4Ag in the prevention of postoperative S aureus SSI occurring within 180 days of elective open posterior instrumented spinal fusion procedures with multilevel instrumentation, in adults 18 to <86 years of age.*

### 2.2.4. Exploratory Objectives

- *To assess the efficacy of SA4Ag in the prevention of postoperative ISA disease occurring within 90 days of elective open posterior instrumented spinal fusion procedures with multilevel instrumentation, in adults 18 to <86 years of age.*
- *To assess the efficacy of SA4Ag in the prevention of postoperative ISA disease occurring within 180 days of elective open posterior instrumented spinal fusion procedures with multilevel instrumentation, in adults 18 to <86 years of age.*
- *To assess the efficacy of SA4Ag in the prevention of postoperative S aureus BSI and/or deep incisional or organ/space SSI occurring within 90 days of elective open posterior instrumented spinal fusion procedures with multilevel instrumentation, in adults 18 to <86 years of age, based on baseline S aureus colonization status.*
- *To assess the efficacy of SA4Ag in the prevention of postoperative S aureus BSI and/or deep incisional or organ/space SSI occurring within 180 days of elective open posterior instrumented spinal fusion procedures with multilevel instrumentation, in adults 18 to <86 years of age, based on baseline S aureus colonization status.*
- *To describe the immunogenicity of SA4Ag in adults aged 18 to <86 years undergoing elective open posterior instrumented spinal fusion procedures with multilevel instrumentation.*
- *To describe S aureus colonization in adults aged 18 to <86 years undergoing elective open posterior instrumented spinal fusion procedures with multilevel instrumentation, before and after SA4Ag administration.*
- *To compare healthcare utilization data between vaccine groups.*

### 3. INTERIM ANALYSES, FINAL ANALYSES, AND UNBLINDING

A conditional power-based futility procedure will be implemented during the earlier stages of primary endpoint case accrual. After accrual of approximately 10, 15, and 24 cases as confirmed by the event adjudication committee (EAC), there will be an assessment of the futility of the study. Only the primary endpoint, defined in [Section 6.1.1](#), will be examined. The sponsor will remain blinded to the case count and will be notified only whether or not the futility threshold has been passed. If the threshold has been passed, then futility may be declared and the study may cease enrollment. Otherwise, enrollment will continue until the next check.

An interim analysis will be performed after accumulating 24 per-protocol (PP) cases that meet the primary efficacy endpoint as confirmed by the EAC. Only the primary endpoint, defined in [Section 6.1.1](#), will be examined. The sponsor will be blinded to the case count, but one of the following outcomes will be reported to the sponsor: (1) lower 99.7% confidence limit on VE exceeds 20%; (2) lower 99.7% confidence limit on VE does not exceed 20%. If the study is not stopped for either futility or efficacy, then the study will continue to the accumulation of 48 cases. Once 48 PP cases have accumulated, SA4Ag will be compared to placebo in analysis of the primary endpoint.

It is anticipated that the immunogenicity analyses will be conducted following database lock. However, an interim immunogenicity analysis may be performed on a subset of subjects prior to the 48th primary endpoint case. The analysis would support regulatory agency interactions for expediting the clinical development of SA4Ag.

The futility checks, the interim efficacy analysis and the interim immunogenicity analysis (if performed) will be compiled by an independent statistical team (IST), in collaboration with the data monitoring committee (DMC).

The sponsor will obtain a snapshot of the database at or near the adjudication of the 48th PP case. After the adjudication, the sponsor will be allowed to unblind the existing snapshot; however, no unblinding information will be communicated to any investigator or subject. The sponsor will then create the unblinded tables, figures, and listings from this unblinded database snapshot. A supplementary clinical study report (CSR) will be produced after all subjects have completed the study.

A database snapshot will also be obtained at or near the adjudication of the 24th PP case. If the study is stopped, then an initial and a supplementary CSR will be created as described above. If the study is not stopped, then no unblinding will occur and the database snapshot will be deleted.

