This is an event-driven study with a total target of 48 primary endpoint *S aureus* cases (meeting the case definition described in [Section 9.1](#)); it is anticipated that approximately 6,000 subjects will be enrolled globally to accumulate these 48 cases. However, the total enrollment number may vary based on the incidence rate of the primary endpoint, true underlying VE, and a potential early stop for efficacy or futility. In the event that efficacy is demonstrated at the interim analysis, enrollment may continue in order to complete the safety evaluations in this surgical population.

There are 5 scheduled study visits and 1 scheduled telephone contact during 6 to 8 months of subject participation. Study-eligible subjects who provided consent will be randomized in a 1:1 ratio to receive a single dose of SA4Ag or placebo at Visit 1, which occurs 10 to 60 days prior to undergoing elective open posterior spinal fusion procedures with multilevel instrumentation (index surgical procedure). Visit 2 is a longitudinal visit and is to monitor the index hospital admission period from the day of surgery (Day 1) until the day of discharge. A telephone contact with the subject will occur on Day 21, while postoperative evaluation study visits will occur on Day 42, Day 90, and Day 180 after surgery.

Unscheduled telephone contacts will be conducted for assessment of severe local reactions, severe fever, and severe systemic events after vaccination. Severe fever and severe local reactions may warrant an unscheduled severe local reaction or fever assessment visit.

Following the index hospital admission, unscheduled visits will be conducted for assessment of suspected BSI and/or SSI events, and to assess hospitalization(s) subsequent to the index hospital admission.

VE will be evaluated by monitoring and assessing the occurrence of protocol-defined infections (PDIs). All BSIs, SSIs, and other ISA infections will undergo adjudication by the EAC. Subjects with EAC-confirmed postoperative *S aureus* BSI and/or deep incisional or organ/space SSI occurring within 90 days after the index surgical procedure will contribute to the primary efficacy endpoint analysis.

INVESTIGATIONAL PRODUCTS

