5.2. Breaking the Blind

The study will be subject, investigator, and sponsor blinded.

At the initiation of the study, the study site will be instructed on the method for breaking the blind for individual subjects. The method will be either a manual or an electronic process. Blinding codes are only to be broken in emergency situations for reasons of subject safety. Whenever possible, the investigator will consult with a member of the sponsor's study team prior to breaking the blind. When the blinding code is broken, the reason must be fully documented in the source notes.

The EAC will receive, review, and adjudicate blinded subject data only.

The data monitoring committee (DMC) will review blinded and unblinded study summary reports. Unblinded study reports will be prepared by an unblinded, independent statistician under the direction of the blinded study statistician. The DMC will also review unblinded study data at the periodic futility checks and at the interim analysis. Details are provided in the DMC charter.

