9.3.3. Analysis of Secondary Endpoints

9.3.3.1. Efficacy

All secondary endpoints will be analyzed using the per-protocol population. The binomial methodology described above will be used to test the null hypothesis of no difference between treatments, with $p = 1/2$ and number of trials set to total number of cases from SA4Ag and placebo. Two-sided p-values of the probability of the indicated SA4Ag cases or fewer will be calculated.

As sensitivity analyses, the secondary endpoints will be evaluated in the mITT populations with $p = 1/2$ and number of trials set to total number of cases from SA4Ag and placebo.

Secondary endpoints will be analyzed only after all subjects have completed the study and the database is locked.

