9.6. Analysis Timing

There will be periodic futility checks after approximately 10 and 15 cases have accrued, and an interim analysis performed after the accrual of 24 cases that meet the primary efficacy endpoint as confirmed by the EAC. The DMC will perform these analyses, in association with the independent statistical team (IST), as required to discharge its responsibilities.

It is anticipated that immunogenicity analyses will be conducted following database lock; however, an interim immunogenicity analysis may be performed on a subset of subjects, if these results are required to support regulatory agency interactions to expedite the clinical development of SA4Ag ([Section 9.3.4.1](#)).

All other analyses will be performed after database lock and unblinding, with the exception of the primary endpoint analysis ([Section 9.3.2](#)).

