9.7. Data Monitoring Committee

This study will use an independent, external data monitoring committee (DMC). Membership and conduct of the DMC is described in a separate DMC charter.

The DMC is responsible for ongoing monitoring of the safety of subjects in the study, and for the assessment of VE/futility, in accordance with the charter. The DMC is also responsible for providing recommendations on the need for adjusting the sample size required to achieve 48 per-protocol cases. The DMC is not specifically responsible for evaluating immunogenicity or *S aureus* carriage data collected as part of the protocol.

The DMC may review unblinded data during closed meeting sessions; however, the sponsor will remain blinded and will not be permitted access to the randomization assignments until the database is locked.

The DMC will review efficacy and safety data at defined intervals as specified in the charter. The DMC may conduct additional meetings to review safety data at other time points during the study, at its discretion, or at the request of the sponsor. In addition, as determined by the sponsor clinician, the DMC may meet on an ad hoc basis to evaluate any SAEs related to vaccination, or related AEs that may jeopardize further subject participation, in order to determine that the study may be continued safely.

The DMC will work in association with the IST in order to conduct both the safety and futility/efficacy evaluations. The IST will include statistician(s) and programmer(s) who are independent of the sponsor and who have unrestricted access to the randomization assignments during the study. The IST will perform statistical analysis and prepare unblinded data and reports to provide to the DMC for assessment in accordance with the DMC charter. The IST will report the outcome of the planned futility checks (only whether the futility rule has been passed or not) to the sponsor and the DMC separately.

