### 5.6.2. Protocol Deviations Occurring After Randomization

1. Vaccinated subjects who do not undergo the planned index surgery will be included only in the safety population.
2. Nonvaccinated subjects will be excluded from all populations.
3. Subjects will be excluded from the PP efficacy population for any of the following reasons:
  - a. Not vaccinated as randomized
  - b. Undergoing index surgery 8 days or sooner after vaccination *or* 91 days or later after vaccination
  - c. Not meeting 1 or more of the study-defined criteria for the index surgery
  - d. Having 1 or more major protocol deviations expected to affect efficacy or immunogenicity, prior to the onset date of suspected *S aureus* infection as determined by a medically qualified clinician at the sponsor
  - e. Suspected or confirmed infection or malignancy identified during the index surgical procedure

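### The SAP lets the sponsor unblind a snapshot while subjects are still in follow-up, but the protocol denies it the assignments until database lock

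*SAP*

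**What the plan says.** **Protocol.** Section 5.2 states: "The study will be subject, investigator, and sponsor blinded". Section 9.7 says that "the sponsor will remain blinded and will not be permitted access to the randomization assignments until the database is locked". Section 9.6 makes one exception on timing: "All other analyses will be performed after database lock and unblinding, with the exception of the primary endpoint analysis". Section 9.7 also allows the split of cases between groups to be disclosed once a permanent stop has been decided. Section 9.3.3.1 adds: "Secondary endpoints will be analyzed only after all subjects have completed the study and the database is locked".

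**SAP.** Section 3 plans a snapshot at or near adjudication of the 48th per-protocol case and then states: "After the adjudication, the sponsor will be allowed to unblind the existing snapshot". The sponsor produces unblinded tables, figures and listings from it, and a supplementary report follows when all subjects have finished. Only investigators and subjects are named as people to be kept uninformed. For the 24th case the route is conditional: "If the study is stopped, then an initial and a supplementary CSR will be created as described above". If the study continues, nothing is unblinded.

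**Sponsor judgement.** SAP 5.6.2 excludes subjects from the per-protocol population for major deviations before infection onset, "as determined by a medically qualified clinician at the sponsor".

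**The concern.** A snapshot is not a lock: the SAP's own supplementary report shows that follow-up is still running when the sponsor unblinds. Listings are subject-level, so this goes well beyond knowing the case split.

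After that point the sponsor still has four kinds of input:

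- judging major deviations that remove later subjects or cases from the per-protocol population (SAP 5.6.2);
- helping investigators supply the supporting documents for adjudication (Protocol 2.5);
- reclassifying a nonserious adverse event as serious (Protocol 8.1);
- making analysis choices meant to follow blinded review, such as the unit for pre-surgery adverse event rates (SAP 8.1.2.1).

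Neither document requires these to be settled before unblinding, and neither describes a sponsor team that stays blinded. At stake are the three secondary endpoints (two run to Day 180), the overrun cases, and the safety data to Day 180.

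**Working it through.** **Step 1. Do the protocol's exceptions reach the SAP rule?**

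| Rule | What it permits before lock |
|---|---|
| Protocol 9.6 | The primary endpoint analysis |
| Protocol 9.7 | Disclosure of the case split after a decision to stop permanently |
| Protocol 9.3.3.1 | Nothing for secondary endpoints |
| SAP 3 | Sponsor unblinding of the whole snapshot, with listings |

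The SAP permission is wider than both exceptions together. Protocol section 9 lets the SAP modify statistical plans. However, where the SAP departs from the protocol on the surgery window (SAP 5.2), it says so. In section 3 it flags no departure.

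**Step 2. Is the primary result sealed before unblinding?** Mostly. Unblinding follows adjudication of the 48th case, and later cases are supplementary (Protocol 9.3.2.1, SAP 4.2). One gap remains. Protocol 9.1 and SAP 8.1.1 also count cases already in the adjudication system on the trigger day if they are confirmed afterwards. Nothing requires those to be adjudicated, or their per-protocol status fixed, before the snapshot is opened.

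**Step 3. What can one case do at the boundary?** Inputs: x SA4Ag cases of n; p = x/n; VE = 1 − p/(1 − p); Clopper-Pearson limits at 95.1% (SAP 8.1.1). The lower VE limit is 1 − pU/(1 − pU), where pU is the upper limit for p. Success requires it to exceed 20%.

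- The plan's own figure, 14/48: VE = 1 − 14/34 = 58.8%; pU = 0.4413; lower limit = 1 − 0.4413/0.5587 = 21.0%. This reproduces Protocol Table 15 (21.0%, 79.6%).
- One placebo case removed, 14/47: VE = 1 − 14/33 = 57.6%; pU = 0.4496; lower limit = 1 − 0.4496/0.5504 = 18.3%. Fails.
- One same-day SA4Ag case confirmed and kept, 15/49: VE = 1 − 15/34 = 55.9%; pU = 0.4548; lower limit = 1 − 0.4548/0.5452 = 16.6%. Fails. If that case were excluded for a major deviation, the count would stay at 14/48 and pass.

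**Step 4. How many subjects are in follow-up at a 48-case snapshot?** Inputs: about 6000 enrolled and 6 to 8 months' participation (Protocol 3.1). The documents give no accrual period, so I assume uniform enrolment over T months. The number still in follow-up is 6000 × m/T, with m = 6 or 8.

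| Assumed T | m = 6 | m = 8 |
|---|---|---|
| 36 months | 1000 (16.7%) | 1333 (22.2%) |
| 48 months | 750 (12.5%) | 1000 (16.7%) |
| 60 months | 600 (10.0%) | 800 (13.3%) |

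**The case against.** The strongest reply is that the people who determine outcomes stay blinded. A reader might infer that an unblinded sponsor decides endpoints. The documents do not support that: Protocol 2.5 makes the blinded committee's classification final, and investigators, also blinded, identify and report infections. What remains is sponsor input to the supporting documents.

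Sponsor discretion over the per-protocol population is also narrow. Vaccination as randomized, the surgery window and the index-surgery criteria are largely factual; the major-deviation criterion is the one SAP 5.6.2 assigns to a sponsor clinician. The same endpoints are repeated in the mITT and restricted mITT populations, which do not use that criterion. This limits the damage, but the per-protocol population is the primary one for all efficacy objectives (Protocol 9.3).

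A reader might also infer that an efficacy interim would put about half the trial under an unblinded sponsor, because the protocol says that "enrollment may continue in order to complete the safety evaluations in this surgical population". That does not follow. At the 24th case SAP 3 allows unblinding only if the study is stopped, and it does not say whether a study still enrolling for safety counts as stopped. This is an ambiguity to resolve, and no figure can be attached to it.

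Finally, SAP 8.1.3.5 records that futility was met at the interim on 20 December 2018 and enrolment ceased, so the 48-case and efficacy branches are closed for the current SAP and no primary success claim is at stake. That is fair. But the unblinding route for a stopped study was open, SAP Amendments 4 and 5 came later, and section 8.1.3.5 still expects that further cases may be found before closeout. The documents do not say whether or when the sponsor unblinded. Access controls may exist in the DMC charter, which is not available here.

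**Conclusion.** The contradiction between SAP 3 and Protocol 9.7 is real, and the protocol's exceptions do not resolve it. Followed as written, the SAP would have a sponsor clinician judge major-deviation exclusions for later cases with treatment assignments accessible. The consequence falls on the secondary endpoints, overrun cases and Day 180 safety data.

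It would be wrong to read this as a general threat to the primary result. That exposure is confined to same-day cases confirmed after unblinding, and it matters only near the boundary, where one case can move the lower limit from 21.0% to 18.3% or 16.6%. The estimate of 600 to 1333 subjects (10 to 22% of 6000) rests on assumed uniform accrual over 36 to 60 months and applies to a 48-case snapshot, not to the stop that occurred. Nothing here shows that any decision was in fact biased.

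**What to change.** 1. Reconcile SAP 3 with Protocol 9.6 and 9.7 so that one rule states who may see assignments, when, and for which analysis.
2. Before any snapshot is unblinded, finish adjudicating the same-day cases. Freeze per-protocol status, deviation classification and the remaining analysis choices for snapshot subjects.
3. Limit unblinded access to the existing independent statistical team or a named, firewalled reporting group. Keep the sponsor's study team, including the clinician who judges deviations, blinded until final lock.
4. State whether a study that continues enrolling for safety after an efficacy interim counts as stopped.

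The cost is document wording, an access memo, and a reporting group kept separate for some months. The case counts, decision boundaries, type I error and power do not change.

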## 4. HYPOTHESES AND DECISION RULES

### 4.1. Statistical Hypotheses

SA4Ag will be compared to placebo testing the hypotheses  $H_0: VE \leq 20\%$  vs  $H_a: VE > 20\%$ .

### 4.2. Statistical Decision Rules

The conditional power-based futility procedure will be performed after accumulating approximately 10, 15, and 24 cases. Only the primary endpoint, defined in [Section 6.1.1](#), will be examined. The power of the study to reject the original null hypothesis, conditional upon the results accumulated so far, will be calculated. Futility may be declared and the study may cease enrollment, if the conditional power falls below 20%. For the planned case totals, the number of vaccine cases which would lead to conditional power below this threshold are shown in Table 1.

**Table 1. Conditional Power at Planned Futility Analyses**

Total Cases	Minimum SA4Ag Cases for futility	Estimated VE (%)	Conditional Power a
10 b	7	-133% (-1298%, 46.7%)	6.9%
15	9	-50% (-412%, 52.3%)	19.4%
24	11	15.4% (-105%, 66%)	16.1%

VE = vaccine efficacy.

- Power of the study to detect  $VE > 20\%$  at the final analysis at 48 cases, conditional upon the cases observed so far, and assuming  $VE = 70\%$  following the futility check.
- For 10 total cases, the SA4Ag case criterion and conditional power were calculated before protocol amendment 4 based on the previous study hypothesis.

Conditional power will be evaluated under the assumption that after the futility check, vaccine efficacy is 70%, as in the main study design assumptions. For operational reasons, the futility checks may occur at slightly different case totals from those planned; in that case, the futility rule of less than 20% conditional power will apply.

The interim efficacy analysis will be performed after accumulating 24 PP cases. Only the primary endpoint, defined in [Section 6.1.1](#), will be examined. The probability of the number of vaccine cases will be calculated using the binomial distribution with 24 trials and  $\pi = 0.444$  because, under the null hypothesis and 1:1 randomization, the probability that a selected case is from the SA4Ag cohort is 0.444. If the number of vaccine cases is 3 or fewer, then the null hypothesis will be rejected in favor of the vaccine. A 99.7% confidence interval (CI) will be obtained for VE.

Once 48 PP cases have accumulated, SA4Ag will be compared to placebo in the primary endpoint. SA4Ag will initially be compared to placebo, testing the hypothesis  $H_0: VE \leq 20\%$  vs  $H_a: VE > 20\%$ . SA4Ag will be deemed efficacious if it has 14 cases or fewer out of a total of 48 cases (point estimate of  $VE \geq 58.8\%$  and 2-sided lower 95.1% confidence limit  $> 20\%$ ).

If study enrollment is stopped for efficacy at the interim analysis, events collected subsequent to the interim analysis will be reported in a supplement in a similar manner to that described by Whitehead for overrunning data. Otherwise, the study will continue to the accumulation of 48 cases. Events collected after the 48th case (or 24th case, if the study ends after the interim analysis) will be analyzed using the method described by Whitehead. This analysis will be considered supplemental. The conclusion from the interim/final analysis will serve as the primary basis for efficacy conclusions.

The interim immunogenicity analysis, if performed, will be limited to group-level statistics and will be conducted by an unblinded team, independent of the sponsor, in order to maintain blinding. All immunogenicity endpoints are defined as exploratory and the study will not be prematurely terminated or altered in any way (eg, no design or operational changes) from the interim immunogenicity analysis; therefore, no type 1 error adjustment is proposed.

